Data for this study will be entered into a REDCap database, which uses a MySQL database via a secure web interface with data checks used during data entry to ensure data quality. REDCap is a free, secure, web-based application designed to support data capture for research studies. The system was developed by a multi-institutional consortium initiated at Vanderbilt University (7).

- *Statistical analysis plan:*

**Power and Sample Size:** The study will recruit 10 study participants. The study is designed to estimate parameters for a detailed power analysis for a further, larger, confirmatory study.

With 10 participants, the half width for the 95% confidence interval for the proportion of examinations with artifacts will be no more than 0.31.

We describe the analysis plan for Hypothesis #4. The other analysis plans are exactly parallel.

We will fit a general linear multivariate model with doubly repeated measures. The three within participant factors are imaging modality, location (hepatic vein, hepatic artery, and portal vein) and reader. The four imaging modalities are Inhance 3D Velocity noncontrast MRA, Inhance Inflow IR noncontrast MRA, postcontrast MRA, and CTA. The eleven locations of measurement are: The proper, right, middle, left hepatic artery, the right portal vein at the branching point from the main portal vein, the main portal vein 1 cm distal to the bifurcation, the right, middle, left hepatic veins, the major branch of the middle hepatic vein draining the right lobe at the insertion to the middle hepatic vein main stem, the accessory hepatic vein at the insertion into the inferior vena cava. We will average across the readers. We will use an alpha-spending approach to assure an overall 0.05 level for the experiment. At the 0.04 level, we will use a Hotelling-Lawley test to assess the null hypothesis of no modality effect on any of the 11 locations of measurement. If there is a difference, we will conduct two step-down tests to assess the difference between Inhance 3D Velocity non-contrast MRA and CTA, and the difference between Inhance Inflow IR non-contrast MRA and CTA. Finally, we will assess the difference between post-contrast MRA and Inhance 3D Velocity noncontrast MRA, the difference between post-contrast MRA and Inhance Inflow IR non-contrast MRA and the difference between post-contrast MRA and CTA.

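### Hypothesis #4: the joint Hotelling-Lawley test over 11 locations cannot be computed with 10 donors (33 contrasts, 9 error df), so the tests that depend on it have no gate

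*Combined protocol and SAP*

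**What the plan says.** The Statistical analysis plan sets the sample size first: "The study will recruit 10 study participants". The purpose it gives is estimation: "The study is designed to estimate parameters for a detailed power analysis for a further, larger, confirmatory study".

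It then writes out the analysis of Hypothesis #4 and says that the analyses of the other outcomes follow the same pattern. The model is a general linear multivariate model with repeated measures. On its factors the plan says: "The three within participant factors are imaging modality, location (hepatic vein, hepatic artery, and portal vein) and reader". It then lists eleven individual measurement sites. Of the five readers it says: "We will average across the readers". No between-donor factor is named.

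On error control: "We will use an alpha-spending approach to assure an overall 0.05 level for the experiment". At level 0.04, "we will use a Hotelling-Lawley test to assess the null hypothesis of no modality effect on any of the 11 locations of measurement". What follows depends on that result: "If there is a difference, we will conduct two step-down tests to assess the difference between Inhance 3D Velocity non-contrast MRA and CTA", together with the matching test for Inhance Inflow IR. Three further comparisons are introduced by: "Finally, we will assess the difference between post-contrast MRA and Inhance 3D Velocity noncontrast MRA". The plan does not say whether these three also require a positive joint test. It gives no reduced set of contrasts, no structured covariance and no fallback. It does promise p-values, estimates and 95% confidence intervals.

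**The concern.** A multivariate test of this kind inverts the error matrix of the contrasts being tested. That requires at least as many error degrees of freedom as contrasts. The contrasts here come from 4 modalities at 11 sites, and the degrees of freedom come from 10 people. If the inversion is impossible, there is no statistic and no p-value.

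The two gated comparisons are the ones closest to the study's purpose, which is to see whether noncontrast MRA can stand in for CTA. If the gate cannot be evaluated, the plan gives no rule for running or withholding them. The stated error level for #4 would then rest on a substitute that the plan does not name.

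**Working it through.** **Inputs**, all from the Statistical analysis plan: N = 10 donors; 4 modalities; 11 locations; readers averaged; no between-donor factor, so the design has rank 1 (intercept only).

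**The plan's own figure.** The only sample-size figure given is a 95% half width of at most 0.31 for the artifact proportion: 1.96 × √(0.5 × 0.5 / 10) = 0.310. It reproduces, but it says nothing about #4.

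**Joint test.**
- Contrasts: p = (4 − 1) × 11 = 33.
- Error df: ν = 10 − 1 = 9.
- The statistic is trace(H E⁻¹), with E a 33 × 33 matrix of rank at most ν. On simulated data with 10 donors, E had rank 9.
- With one hypothesis df the test reduces to Hotelling's T², with denominator df ν − p + 1 = 9 − 33 + 1 = −23. No such distribution exists.
- Smallest N: ν ≥ p gives N ≥ 34. The simulated rank was 32 of 33 with 33 donors and 33 of 33 with 34.

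**Step-down tests, if they span the 11 locations.** Contrasts (2 − 1) × 11 = 11 on 9 df; rank 9; denominator df 9 − 11 + 1 = −1. These do not exist either, and would need at least 12 complete donors.

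**Readings that might rescue the joint test.**

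| Reading | Contrasts | Denominator df (ν = 9) | Result |
|---|---|---|---|
| Readers not averaged | 3 × 11 × 5 = 165 | −155 | not computable |
| Without the middle hepatic vein branch and the accessory vein | 3 × 9 = 27 | −17 | not computable |
| Three vessel groups | 3 × 3 = 9 | 1 | F(9,1), critical value 376 at 0.04 |
| Locations averaged | 3 | 7 | F(3,7), critical value 4.81 at 0.04; a different null |

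The three-group reading matches the parenthesis in the list of factors, but the stated null names 11 locations. At noncentrality 50 its power is about 0.10, and one incomplete donor makes it singular (rank 8 of 9). Treating donor-by-modality as the unit gives (10 − 1) × (4 − 1) = 27 error df for 11 responses. That is computable, but it needs a covariance assumption that the plan does not state.

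**Other outcomes.** Outcomes with one value per modality, such as #1 and #5, have 3 contrasts on 9 df and are not affected. Relative signal intensity (#7) covers three MR techniques. If it is taken at the same 11 sites, which is an assumption because the plan does not say, it has (3 − 1) × 11 = 22 contrasts on 9 df and the same problem.

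**The case against.** The strongest defence is that this is a pilot whose declared purpose is to supply parameters for a later non-inferiority study. Means, single-contrast variances and per-location 95% confidence intervals need no inversion of the 33 × 33 matrix. That defence stands and limits the consequence. It does not remove the defect, because the plan also chose formal hypothesis tests with an experiment-wise level, and #4 is the analysis it writes out as the model for the rest.

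Four stronger readings are tempting, and the documents do not support them.
- A reader might infer that the pilot fails. Its estimation aim does not depend on the joint test.
- A reader might infer that the analyst must pick a substitute after seeing the data. The singularity follows from the dimensions alone, so a substitute can be fixed beforehand.
- A reader might infer that the plan's false-positive rate is inflated by a calculable amount. A test that cannot be run has no error rate, and any such figure would describe a substitute that the plan does not propose.
- A reader might infer that all five pairwise comparisons are blocked. Only two are expressly conditional; the status of the other three is unclear.

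Nor can the problem be confined to #4, since the other analyses are said to follow the same pattern.

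**Conclusion.** Wrong as written, and correctable by wording. The joint test for #4 asks for 33 contrasts from 9 error df and does not exist below 34 complete donors. The two conditional comparisons with CTA have no computable gate and, if they span the 11 locations, are not computable themselves. The p-values of this test sequence and the overall 0.05 level for #4 cannot be delivered as the plan stands. Any other outcome analysed over many locations shares the problem; single-value outcomes do not.

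The conclusion assumes one row per donor, an intercept-only design, reader averaging and complete data, as the plan describes. Missing vessels would only reduce the 9 df. This should be settled before analysis; it does not defeat the study.

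**What to change.** Amend the SAP before any measurement is analysed, by one of two routes.

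**(a) Estimation only.** Drop the joint test for #4. Report modality differences per location with 95% confidence intervals as the pilot output, and make no experiment-wise 0.05 claim for #4. This is the simpler route and fits the stated purpose. Its cost is that #4 has no formal test.

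**(b) Tests by location.** Use one 3-contrast Hotelling-Lawley test per location on reader averages, F(3,7) with 10 complete donors, for a named measure. List the family of m locations by name and test each at 0.04/m. Where a location is significant, run the plan's pairwise comparisons there, adjusted within the location (Holm, for example) at the same carried-over 0.04/m. A location with no modality effect can err only through its own test, and one with an effect only through its adjusted pairs. The total is therefore at most m × 0.04/m = 0.04 under any correlation. The text must also state:
- what the remaining 0.01 is for;
- whether the three final comparisons are gated;
- which donors enter each location test and each pairwise test when a vessel is absent or unmeasurable on a modality;
- that unmeasurable vessels are reported by modality, because leaving those donors out would hide a technique's failures.

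Route (b) has low power. With m = 9, for example, the critical value is 11.35 and power is 0.11 and 0.81 at noncentrality 10 and 50. At the same per-donor effect, the 0.81 falls to 0.65, 0.45 and 0.26 with 9, 8 and 7 complete donors.

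Under either route, say how #7 and any other multi-location outcome will be handled. Neither route needs new scans or readings.
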